1. Total Suturing time for mesh placement = time from insertion of Y mesh or first flat mesh arm into pelvis to last sacral suture placed
2. Total OR time = operating room time of entry and exit
3. Total Case time = Incision to end of closure

Secondary Outcomes:

1. Intraoperative, peri-operative and post-operative complications
2. Hospital costs (Y mesh v. dual mesh and stratified by RA LSC v. LSC)
3. Post-operative patient outcomes at 6 weeks, 6 months, 12 months and 24 months
 - Pelvic Organ Prolapse Quantification (POPQ) system (standardized quantification of prolapse established by the International Continence Society) – Required at 6 months; Optional but encouraged at 12 and 24 months.
 - Pelvic Floor Dysfunction Inventory (PFDI-20) – Required pre-operatively and at 6 weeks, 6, 12 and 24 months.

Study Population: Study subjects will be recruited from patients that present to the Center of Urogynecology and Pelvic Floor Disorders in the Department of Obstetrics and Gynecology at the Cleveland Clinic main campus, Hillcrest Hospital and Fairview Hospital, and their surgeries will be performed at either one of these sites.

Inclusion Criteria:

- Age \geq 18, who are to undergo laparoscopic or robotic laparoscopic sacrocolpopexy for pelvic organ prolapse
- Other concomitant laparoscopic or prolapse and anti-incontinence procedures (e.g., laparoscopic supracervical hysterectomy, cystocele repair, rectocele repair or mid-urethral sling procedures) will be performed at the primary surgeon's discretion.

Exclusion Criteria:

- Inability to comprehend written and/or spoken English
- Inability to provide informed consent
- Medical illness precluding laparoscopy
- Need for concomitant surgeries not related to pelvic organ prolapse or incontinence
- Sacrocolpoperineopexy

Study Procedures:

Study Identification and Recruitment

Potential subjects will be identified by members of the Center for Urogynecology and Pelvic Reconstructive Surgery at the Cleveland Clinic main campus and Fairview Hospital. Eligible patients that agree to participate will be provided written informed consent administered by the collaborators listed on this IRB at the Cleveland Clinic main campus and Fairview Hospital.

Randomization

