- The stem portion of the graft is then brought to the sacral promontory and sutured to the anterior longitudinal ligament using 2 permanent (prolene) No. 0 sutures. The excess mesh is then trimmed.

2. Restorelle dual flat mesh: 2 pieces of 15 x 4 cm mesh

- One mesh arm is introduced into the pelvis through one of the ports.
- The arm is fixed to the anterior or posterior vaginal wall using 5 delayed- absorbable (PDS) No. 2-0 sutures in an interrupted fashion, 1 to 2 cm apart from each other.
- The second mesh arm is then introduced into the pelvis through one of the ports.
- The arm is fixed to either the anterior or posterior vaginal wall, depending on where the first arm was placed, using 5 delayed- absorbable (PDS) No. 2-0 sutures in an interrupted fashion, 1 to 2 cm apart from each other.
- The two arms are then brought to the sacral promontory and sutured together to the anterior longitudinal ligament using 2 permanent (prolene) No. 0 sutures. The excess mesh is then trimmed.

The peritoneum is then closed over the exposed graft with absorbable suture.

Routine cystoscopy will also be performed in order to assess for lower urinary tract injury. A vaginal exam is performed, and an anterior and/or posterior colporrhaphy and perineorrhaphy are performed if needed. Anti-incontinence procedures may also be performed if needed.

**In laparoscopic cases, all suturing will be done extracorporeally while intracorporeal knot-tying technique will be performed in robot assisted laparoscopic cases.

Data Collection & Management:

Preoperative data will include the following:

- Patient age, race, vaginal parity, menopausal state, BMI, prior prolapse surgery, preoperative prolapse stage
- PFDI-20
- Labs (Hb/Hct)

Data points recorded during the procedure will include:

- Total OR time = operating room time of entry and exit
- Total Case time = time from incision to closure
- Total Suturing time = time from insertion of Y mesh or first flat mesh arm into pelvis to last sacral suture placed
- Level of surgeon performing suturing: Attending v. Fellow v. Both
- Concomitant procedures
 - Hysterectomy – Supracervical or Total
 - Anterior Colporrhaphy
 - Posterior Colporrhaphy
 - Perineorrhaphy
 - Midurethral Sling
- Estimated blood loss
- Intraoperative complications
 - EBL > 500cc
 - Vascular Injury
 - Cystotomy
 - Ureteral Injury
 - Bowel Injury - small bowel, large bowel, rectal

Postoperative data will include the following:

- Days in the hospital

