We will use descriptive statistics to show our demographic and baseline data: categorical variables will be presented as n/N (%) with 95% confidence intervals and continuous variables will be presented as mean+/-SD [range]. Y mesh and dual mesh will be compared between the two groups (Y mesh LSC + RA LSC v. Dual mesh LSC + RA LSC). With a continuous outcome and two categorical independent factors, a two-way

analysis of variance will be used to evaluate differences between the groups. The results will be presented in a standard ANOVA table, which should be sufficient to determine if differences exist. A linear regression will be done to demonstrate actual changes in surgical time attributed to each variable. We will control for LSC ASC and RA LSC ASC by performing a logistic regression. Cost utility analysis will be used to compare the differential mean operating room costs with incremental cost effectiveness ratios (ICERs) calculated as appropriate.

Summary of tasks for study:

	Preop	O R	6 wk postop	6 mo f/u	12 mo f/u	24 mo f/u
Informed consent	X					
Demographic data	X					
Randomization	X					
PFDI-20	X		X	X	X	X
POP-Q	X			X	X ¹	X ¹
OR data collection sheet		X				
Review of d/c summary, chart, postop Hct, complications (ER visits, etc)			X	X	X	X

1. **POP-Q – Optional but encouraged at 12 and 24 months.**

References:

3. Porges RF & Smilen SW. Long term analysis of the surgical management of pelvic floor support defect. *Am J Obstet Gynecol* 1994;171:1518–1528.
4. Birch C. The use of prosthetics in pelvic reconstructive surgery. *Best Pract Res Clin Obstet Gyn* 2005;19(6):979-991.
5. Chu CC & Welch L. Characterisation of morphological and mechanical properties of surgical mesh fabrics. *J Biomed Res* 1985;19:903–916.
6. Kaupp HA, Matulewicz TJ & Lattimer GL. Graft infection or graft reaction? *Arch Surg* 1979;114:1419-1423.

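### Total OR time and total case time include discretionary concomitant surgery that the two-factor ANOVA leaves in its error term: a loss of precision, not a bias

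*Combined protocol and SAP*

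**What the plan says.** **Outcomes.** The Primary Outcomes section lists three times.
- Suturing time is the "time from insertion of Y mesh or first flat mesh arm into pelvis to last sacral suture placed".
- The second outcome reads "Total OR time = operating room time of entry and exit".
- The third reads "Total Case time = Incision to end of closure".

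**Concomitant surgery.** The Inclusion Criteria state that "Other concomitant laparoscopic or prolapse and anti-incontinence procedures" (the examples are supracervical hysterectomy, cystocele repair, rectocele repair and mid-urethral sling) "will be performed at the primary surgeon's discretion". Surgical Interventions describes any hysterectomy before the sacrocolpopexy. After the mesh is fixed and a vaginal exam is done, "anterior and/or posterior colporrhaphy and perineorrhaphy are performed if needed", and anti-incontinence procedures may follow on the same basis.

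**Randomization and data.** Randomization is by provider. Concomitant procedures are recorded among the operative data. The pre-operative data list has no field for planned procedures.

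**Analysis.** The Analysis Plan begins "With a continuous outcome and two categorical independent factors" and chooses a two-way ANOVA, to be shown in "a standard ANOVA table, which should be sufficient to determine if differences exist". The two factors are not named. The four-arm layout (two meshes by two routes) points to mesh and route. A linear regression is also planned, to show how much surgical time each variable accounts for, but it has no covariate list. A further regression is meant to control for route only.

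**The concern.** The windows for OR time and case time run through every concomitant procedure. A hysterectomy lengthens both for reasons unrelated to the mesh, and surgeons choose it patient by patient. A model with only mesh and route treats that variation as unexplained error. Nothing in the randomization balances hysterectomy between the mesh groups within a provider.

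What is at stake is the power of two outcomes labelled primary, neither of which has a sample-size basis. The Background asks whether any time saved in suturing becomes a saving in the operating room. OR time and case time are the outcomes closest to that question, so variance that could be removed cheaply is worth removing.

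**Working it through.** **The plan's own figure.** The Analysis Plan gives 9 subjects per arm for a 30-minute difference in suturing time, with 80% power and a significance level of .05. It states no SD, so the figure cannot be reproduced. Solved backwards and two-sided, it implies an SD of 22.7 minutes (normal approximation) or 21.3 (t) at 9 v 9, and 32.1 or 31.2 at 18 v 18. These values concern suturing time and cannot be carried over to OR or case time.

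**Inputs**
- From the documents: 15 per arm in 4 arms, so 30 per mesh group. A four-cell ANOVA has 60 − 4 = 56 error degrees of freedom.
- Assumed, because the documents are silent: hysterectomy prevalence p = 0.5; added time d = 30-60 minutes; SD of OR or case time within the mesh-by-route cells, s = 45-75 minutes.

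**Variance explained.** A yes/no procedure with prevalence p that adds d minutes contributes p(1−p)d² to the variance. With p = 0.5, R² = 0.25d²/s². The gain from adjusting, as equivalent extra patients, is 1/(1−R²) − 1.

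| s | d | R² | Gain |
|---|---|---|---|
| 75 | 30 | 225/5625 = 0.04 | 4% |
| 60 | 30 | 225/3600 = 0.06 | 7% |
| 60 | 60 | 900/3600 = 0.25 | 33% |
| 45 | 60 | 900/2025 = 0.44 | 80% |

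**Detectable difference.** For 30 v 30, two-sided 0.05 and 80% power, the noncentral t gives about 0.736 × SD (56 degrees of freedom unadjusted, 55 adjusted).
- s = 60, d = 60: unadjusted 0.736 × 60 = 44 minutes. The adjusted SD is √(3600 − 900) = 52.0, so 0.736 × 52.0 = 38 minutes.
- s = 75, d = 30: unadjusted 0.736 × 75 = 55 minutes. The adjusted SD is √(5625 − 225) = 73.5, so 0.736 × 73.5 = 54 minutes.

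**Power for a 30-minute difference.** The plan uses 30 minutes only for suturing time; it is borrowed here for scale. The adjusted range is for d = 30 to d = 60.

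| s | Unadjusted | Adjusted |
|---|---|---|
| 45 | 72% | 77-93% |
| 60 | 48% | 50-59% |
| 75 | 33% | 34-38% |

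**Is chance imbalance a separate problem?** The SD of the difference in hysterectomy proportion between mesh groups is √(2 × 0.25/30) = 0.129. Multiplied by d, that is 3.9 to 7.7 minutes. The unadjusted standard error of the mesh difference is s√(2/30), or 11.6 to 19.4 minutes, and it already contains this component. At s = 60 and d = 60, 15.5² − 7.7² ≈ 180 = 13.4², and 13.4 is the adjusted standard error (52.0 × √(2/30)). The imbalance is therefore the same variance that was counted above, not an addition to it.

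**Is suturing time affected?** Its window opens when the mesh enters the pelvis, after dissection and any hysterectomy. It closes at the last sacral suture, before the vaginal repairs. Concomitant surgery lies outside it.

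**The case against.** **The planned linear regression may already cover this.** The procedures are recorded, and the regression could include them. The plan does not make the ANOVA the sole decision rule in so many words. This stands in part. However, the regression is given the job of describing contributions to surgical time, while the ANOVA table is the one called sufficient to show whether differences exist. A regression with no covariate list also leaves the choice of terms until after the data are seen, and it could take in repairs decided after the mesh is in place.

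**Nothing is invalid.** This stands. A reader might infer that an imbalance in hysterectomy could pass for a mesh effect, so that the ANOVA is biased. The documents do not support that: mesh is randomized, the type I error is held, and the standard error already allows for such imbalance.

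**The trial turns on suturing time.** This also stands. The objective, hypothesis and sample size concern that outcome alone. A reader might infer that the trial's main comparison is weakened, but its time window rules this out.

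**The size is assumed and may be trivial.** This stands too. At the low end of the range the gain is 4%. At an SD of 60 or 75 minutes, power for a 30-minute difference stays below 60% with or without adjustment. The case for acting rests on the very low cost, not on a demonstrated large loss.

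**Conclusion.** The point holds as one of efficiency. Two of the three listed primary outcomes carry variation from discretionary surgery that the stated test does not remove, although part of it could be removed safely. The comparison remains valid without adjustment.

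The gain is equivalent to between 4% and 80% more patients, assuming half the women have a hysterectomy, 30-60 added minutes and an SD of 45-75 minutes. None of these inputs is in the documents. The conclusion also rests on reading the unnamed ANOVA factors as mesh and route.

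A reader might go further and ask for adjustment for every procedure performed. The surgical description argues against that. Colporrhaphy, perineorrhaphy and any sling decided on during surgery come after mesh placement and could depend on the mesh. Conditioning on them could remove or distort part of the effect being tested.

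**What to change.** 1. Add planned hysterectomy (yes/no) to the pre-operative form, completed before randomization. Patients are blinded but surgeons are not said to be, so the timing of this entry matters.
2. Name the ANOVA factors. For total OR time and total case time, pre-specify a linear model with mesh, route and planned hysterectomy as the test of the mesh effect.
3. Decide now, before any data are seen, whether planned sling is also a term. If it is, record it on the same form. Do not make its inclusion depend on how common it turns out to be.
4. State that this test is not adjusted for procedures decided during surgery after mesh placement (colporrhaphy, perineorrhaphy or an unplanned sling). Report these descriptively by mesh group.
5. List the covariates of the additional linear regression.

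The analysis of suturing time needs no change on this account. The cost is one form field, or two with sling, and one or two of about 56 error degrees of freedom. Clinical care is unchanged.

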All subjects will be predetermined by their surgeon to undergo either a laparoscopic or robotic assisted laparoscopic sacrocolpopexy depending upon their clinical evaluation. The participants will then be randomized to either Y mesh or dual flat mesh sacrocolpopexy according to a computer-generated randomization schedule with random block sizes with the use of the SAS statistical software package (SAS Institute, Cary, NC). Randomization will be carried out by provider. All patients will be blinded to their assignment.

Office Interventions

In addition to a standardized evaluation including the history and physical examination, patients will be asked to complete the Pelvic Floor Distress Inventory (PFDI-20) questionnaire at the pre-operative visit as well as the 6 week, 6, 12 and 24 month postoperative visit. Completion of these questionnaire is the only additional assessment that is specific to participation in this study and is not usually included as part of the standard care of sacrocolpopexy. It should take no more than 10-15 minutes to complete the questionnaire. The study subjects will not be exposed to any additional risk by participating in this study except for the inconvenience of completing the questionnaire.

Surgical Interventions

Laparoscopic sacrocolpopexy will be performed using four ports: an umbilical port for the laparoscope, two ports (either 5 or 10/12 mm) in the bilateral lower quadrants, and one 5-mm port placed at the level of the umbilicus, lateral to the rectus muscle on either side for retraction. The robotic-assisted hysterectomy will be performed using the da Vinci Surgical System (Intuitive Surgical Inc., Sunnyvale, CA, USA) using five ports: a 12mm umbilical port for the laparoscopic, two 8 mm robotic ports placed 2cm inferior and 9-10cm lateral to the umbilicus bilaterally, an 8mm robotic port placed in the left axillary line at the level of the umbilicus, and a 8mm or 10/12mm accessory port either in the right upper quadrant approximately 3cm distal from the costal margin, or in the right lower quadrant, 2cm above and medial to the anterior superior iliac spine.

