All paper forms used for data collection will be kept in a research cabinet dedicated to this project which will be locked at all times, in a locked office at the Cleveland Clinic. All forms will contain de-identified information – identification numbers will correspond to the subjects listed in the master excel file.

All study data will be transferred and managed electronically using REDCap (Research Electronic Data Capture). Each subject will be entered into REDCap using the assigned identification number from the master excel file. REDCap is a secure, web-based application designed to support data capture for research studies, providing user-friendly web-based case report forms, real-time data entry validation, audit trails, and a de-identified data export mechanism to common statistical packages. The system was developed by a multi-institutional consortium which was initiated at Vanderbilt University and includes the Cleveland Clinic. The database is hosted at the Cleveland Clinic Research Datacenter in the JJN basement and is managed by the Quantitative Health Sciences Department. The system is protected by a login and Secure Sockets Layers (SSL) encryption. Data collection is customized for each study as based on a study-specific data dictionary defined by the research team with guidance from the REDCap administrator in Quantitative Health Sciences at the Cleveland Clinic.

Analysis Plan:

There will be 4 arms to this study: laparoscopic (robotic-assisted and conventional) sacrocolpopexy with Y mesh and laparoscopic (robotic-assisted and conventional) sacrocolpopexy with dual flat mesh. Subjects will be chosen based on surgeon preference to either undergo RA LSC ASC or conventional LSC ASC. They will then be randomized to either a Y mesh arm or a Dual Mesh arm. We determined that 9 subjects in each arm were needed to detect a difference of 30 minutes or more in suturing time between the two groups with 80% power and a significance level of .05. We will account for potential subject drop out and loss to follow-up as well as unforeseen factors in recruiting and will plan to recruit 15 subjects to each arm, for a total of 60 subjects.

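### If mesh is randomised within provider, the time models should include provider; mesh and route alone can overstate the standard error of the mesh difference, a modest error in the conservative direction

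*Combined protocol and SAP*

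**What the plan says.** The Randomization section allocates Y or dual flat mesh "according to a computer-generated randomization schedule with random block sizes" and adds: "Randomization will be carried out by provider". It does not say whether provider is a stratum, how many providers take part or how many cases each contributes.

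Route (robotic or conventional) is not randomised. The Analysis Plan states: "Subjects will be chosen based on surgeon preference to either undergo RA LSC ASC or conventional LSC ASC".

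For the time outcomes the Analysis Plan begins: "With a continuous outcome and two categorical independent factors, a two-way" analysis of variance. From context the two factors are mesh and route. It continues: "A linear regression will be done to demonstrate actual changes in surgical time attributed to each variable", without listing the variables. Route is the only variable named for control: "We will control for LSC ASC and RA LSC ASC by performing a logistic regression". Provider is named in none of these analyses.

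Among the intraoperative data points, Data Collection & Management lists "Level of surgeon performing suturing: Attending v. Fellow v. Both". It does not list which provider's case it was.

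**The concern.** When treatment is balanced within a grouping factor, differences between the groups cancel out of the treatment comparison. A model that omits the factor still counts those differences as residual error, so the SE it reports is larger than the real variability of the estimate. The test then rejects less often than its nominal level, and the confidence interval is wider than its stated coverage requires.

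Three conditions must all hold here: allocation is stratified by provider, times differ between providers, and route does not already stand in for provider. The documents establish none of them, though the first is the likeliest reading of the text. The stake is the calibration of the SE, test and interval for the mesh difference in suturing, OR and case time.

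**Working it through.** **Inputs from the documents.** 60 patients, so 30 v 30 for mesh pooled over route; 9 per arm for a 30-minute difference at 80% power and a 5% level.

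**Inputs that must be assumed.** Number of providers k; provider share of variance ρ (10, 20 or 30%); how closely route follows provider; and the SD.

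**Step 1: the plan's own figure.** No SD is given, so the 9 per arm cannot be reproduced. It can only be solved backwards (two-sided t-test):
- 9 v 9: standardised difference 1.407, so SD = 30/1.407 = 21.3 min.
- 18 v 18 (9 in each of four arms, pooled over route): standardised difference 0.961, so SD = 30/0.961 = 31.2 min.

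The SE ratios below do not depend on the SD.

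**Step 2: approximate SE ratio by hand.** Take k equal-sized providers with mesh balanced within each. The SE from mesh + route, relative to the SE with provider added, is about

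sqrt{ 1 + [ρ/(1−ρ)] × m × N/(N−3) }, with N = 60,

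where m = (k−1)/k if route is unrelated to provider and m = (k−2)/k if each provider uses one route. At ρ = 20%, ρ/(1−ρ) = 0.25 and N/(N−3) = 60/57 = 1.053:
- k = 6, route unrelated: sqrt(1 + 0.25 × 0.833 × 1.053) = 1.104.
- k = 6, one route each: sqrt(1 + 0.25 × 0.667 × 1.053) = 1.084.
- k = 3, one route each: sqrt(1 + 0.25 × 0.333 × 1.053) = 1.043.
- k = 2, one route each: m = 0, ratio 1.000. Route is provider, and nothing changes.

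**Step 3: simulation.** 10,000 trials per setting; random blocks of 2, 4 or 6 within provider; normal provider effects and errors; least squares with and without provider indicators. SE ratio (without/with provider), equal volumes:

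| Providers | Route pattern | ρ = 0 | 10% | 20% | 30% |
|---|---|---|---|---|---|
| 3 | unrelated to provider | 0.999 | 1.036 | 1.079 | 1.128 |
| 3 | 85/15 by provider | 0.995 | 1.024 | 1.057 | 1.099 |
| 3 | one route each | 1.000 | 1.019 | 1.042 | 1.069 |
| 6 | unrelated to provider | 0.996 | 1.042 | 1.097 | 1.162 |
| 6 | 85/15 by provider | 0.992 | 1.034 | 1.083 | 1.141 |
| 6 | one route each | 0.997 | 1.036 | 1.080 | 1.132 |
| 2 | one route each | 1.000 | 1.000 | 1.000 | 1.000 |

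These agree with Step 2. Including unequal volumes, the excess for 3-6 providers over all route patterns is about 1-4% at a 10% share, 3-10% at 20% and 5-16% at 30%.

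**Step 4: is it the SE or the estimate that changes?** The true sampling SD of the mesh estimate without provider is about 1.00-1.02 times that with provider. Measured against its own sampling SD, the SE without provider is 3-9% too large at a 20% share and 5-15% at 30%. The reported SE is wrong; the estimate hardly changes.

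**Step 5: consequences (3-6 providers).**
- Type I error without provider: about 4-5%, 3-4% and 2.5-4% at shares of 10, 20 and 30%. With provider: about 5%.
- 95% CI half-width at SD 21.3 (about 10-11 min): narrower by 0.2-0.4, 0.3-0.9 and 0.4-1.5 min once provider is included. At SD 31.2 (about 14-16 min): by 0.2-0.6, 0.4-1.2 and 0.7-2.0 min.
- Power at 30 minutes: above 99.9% either way at SD 21.3, and 95-99% either way at SD 31.2.

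**Step 6: the other reading.** If allocation is not stratified by provider, the SE without provider is 0.99-1.01 of its sampling SD and type I error is 4.5-5.2%. The planned SE is then valid.

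**The case against.** The strongest case is that the text shows only one unclear sentence. It could mean that the provider carries out the allocation, in which case the planned SE is sound. That stands, and it is why the point is conditional. A computer-generated blocked schedule nevertheless makes one list per provider the more natural reading.

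Four stronger readings are tempting, and the documents do not support them:
- A reader might infer that provider will be left out. The linear regression has no variable list and could include it. All that can be said is that no analysis names it.
- A reader might infer that provider is not recorded. The same data list omits route and assigned mesh, which the analysis plainly needs, so absence from it proves little. A list kept per provider would itself identify the provider.
- A reader might call this lost efficiency. The true sampling SD barely moves (Step 4), so the fault is an overestimated SE.
- A reader might infer bias or false positives. Neither arises; the error runs towards caution.

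It is also fair to say that the provider share for suturing time may be low: suture number, type and spacing are fixed, and a fellow may do the suturing. For OR and case time the share is a separate unknown. The Inclusion Criteria say that concomitant procedures "will be performed at the primary surgeon's discretion", which makes provider differences there plausible but does not show them.

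**Conclusion.** The point holds conditionally and is minor. Its size, a 1-16% larger SE and a type I error of about 2.5-5%, rests on assumed values: 3-6 providers and shares of 10-30%. At a 50% share with 4-6 providers, type I error would fall to about 1.4-2.6%, but nothing in the documents points to a share that large. With two providers using one route each, the effect disappears.

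It still merits a change, because the Analysis Plan should follow the groups that the trial randomises by, and the sentence needs clarifying under either reading.

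**What to change.** State in the Randomization section what the provider sentence means.

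**If stratified:** say that randomisation is stratified by provider with one blocked list each. Carry the provider stratum from the list into the dataset. Analyse suturing, OR and case time as time ~ mesh + route + provider (provider fixed, or random if there are many low-volume providers), and report the adjusted mesh difference with its 95% CI.

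**If not stratified:** correct the sentence. A provider term is then only an optional gain in precision.

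**Cost:** one sentence, one data field, and about one degree of freedom per provider beyond the first. If providers do not differ, intervals widen by about 0-1% with 3-6 providers and 1-3% with 10. If each provider uses one route, route is aliased with provider and drops out of the fixed-effect model. The mesh difference is still estimable, but any route effect then needs a separate model, which matters because the Analysis Plan wants time attributed to each variable.

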- 6-week postoperative visit: PFDI-20
- 6-month postoperative visit (Required): POP-Q exam (performed by a provider blinded to the mesh used at the time of the procedure)
- 12 month, 24 month postoperative visit (Optional): POP-Q exam (performed by a provider blinded to the mesh used at the time of the procedure)
- 6-month, 12-month, 24-month postoperative visit: PFDI-20

- At 6, 12 and 24-months: Review of electronic medical record (inpatient notes, d/c summary, ER visits), assessing for postoperative complications
 - Reoperation for immediate complications = reoperation within 30 days of surgery
 - Abdominal Wound infection = fascial, subcutaneous, cutaneous infection requiring antibiotic treatment
 - Hematoma = intrapelvic/abdominal
 - Vaginal cuff cellulitis/Pelvic Abscess = requiring IV/PO antibiotic therapy and/or transvaginal, transgluteal or percutaneous drainage
 - DVT/PE = diagnosed with Doppler US or CT scan
 - Reoperation for SUI with pubovaginal sling (synthetic or fascial), colposuspension, injection with periurethral bulking agents
 - Reoperation for mesh exposure
 - Reoperation for recurrent POP
 - Bowel Injury/Bowel Obstruction = enterotomy, perforation, ileus, partial/complete obstruction
 - Port site or incisional hernia
 - Need for any radiologic imaging
 - Lower urinary tract injury = bladder, ureteral
 - Neurologic Injury = brachial plexus, abdominal wall (ilioinguinal, iliohypogastric), lower extremity (femoral, sciatic, common peroneal)
 - Pulmonary complications = pneumonia, pulmonary hypertension, pulmonary edema within 14 days of surgery
 - Cardiac = ACS, MI, HF within 14 days of surgery
 - Postoperative ICU admission

[figure not shown]
Protection of each subject's personal health information will be a priority in this study. One master excel file containing subject personal information including name and medical record number will be kept in a password-protected file, on a designated protected research drive on a password-protected computer in a locked office at the Cleveland Clinic. In that file, each subject will be assigned a subject identification number that will be used for the purposes of data collection in order to de-identify subjects.

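### A pre-operative POP-Q is scheduled for every woman, but the data list names only prolapse stage and the one stated model for a continuous outcome has no baseline term, so a 6-month POP-Q comparison made with it would give up some precision

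*Combined protocol and SAP*

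**What the plan says.** **What is measured.** The table headed "Summary of tasks for study" marks POP-Q at the pre-operative visit without a footnote; only the 12- and 24-month marks are footnoted as optional. Under Secondary Outcomes, POP-Q is "Required at 6 months; Optional but encouraged at 12 and 24 months". The postoperative data list repeats this: "6-month postoperative visit (Required): POP-Q exam", by an examiner blinded to the mesh.

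**What is listed as baseline data.** The preoperative list under Data Collection & Management ends its patient characteristics with "prior prolapse surgery, preoperative prolapse stage". It does not name POP-Q measurements. PFDI-20 is handled differently: it is "Required pre-operatively and at 6 weeks, 6, 12 and 24 months" under Secondary Outcomes, and it appears by name in the preoperative list.

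**What is modelled.** The Analysis Plan states one group comparison: "With a continuous outcome and two categorical independent factors, a two-way" analysis of variance. From the context the two factors are mesh and route (conventional or robotic-assisted). It then adds: "A linear regression will be done to demonstrate actual changes in surgical time attributed to each variable". A logistic regression is mentioned to control for route. No baseline covariate or change score appears, and neither POP-Q nor PFDI-20 is given an analysis by name.

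**The concern.** The 6-month POP-Q is the only required postoperative anatomical exam. A trial that asks whether one graft is faster to place will also want to show whether the two support equally well, and this exam bears directly on that.

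About 30 women per mesh is a small comparison. Randomisation is by provider, in blocks of varying size, and no stratification by prolapse severity is described. Chance differences in starting anatomy are therefore not controlled by design. If pre-operative and 6-month values are correlated, part of such a difference carries into the 6-month comparison, and variance that the baseline could explain stays in the error term. The baseline exam is already scheduled, so using it needs no new assessment.

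**Working it through.** **The plan's own figure.** No sample size, SD or detectable difference is given for POP-Q. The only size calculation concerns suturing time: "9 subjects in each arm were needed to detect a difference of 30 minutes or more in suturing time between the two groups". Without an SD it can only be solved backwards: two-sided and by the normal formula, SD = 30 / [(1.960 + 0.842) × √(2/9)] = 22.7 minutes. It has no bearing on POP-Q.

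**Inputs for POP-Q.**
- From the Analysis Plan: 4 arms × 15 = 60 women, so 30 per mesh when route is pooled.
- Assumed, because the documents do not give it: correlation r between the pre-operative and 6-month values of the same measurement, 0.2 to 0.5.
- Assumed: two-sided 5% level and 80% power, for the detectable difference.

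**Variance removed.** A baseline covariate multiplies the residual variance by (1 − r²). The equivalent unadjusted size is 60 / (1 − r²).

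| r | Variance removed | Equivalent total |
|---|---|---|
| 0.2 | 4% | 62.5 |
| 0.3 | 9% | 65.9 |
| 0.4 | 16% | 71.4 |
| 0.5 | 25% | 80.0 |

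Estimating the extra coefficient offsets a little of this. With mesh and route in the model there are 60 − 3 = 57 residual degrees of freedom, and the variance of the mesh effect rises by about 1/(57 − 2) = 1.8%. The net factor is about 0.96 × 1.018 = 0.98 at r = 0.2 and 0.75 × 1.018 = 0.76 at r = 0.5.

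**Detectable difference**, before that offset: (1.960 + 0.842) × √(2/30) × √(1 − r²), in SDs of the 6-month value.
- No baseline term: 0.72 SD.
- r = 0.2: 0.71 SD.
- r = 0.5: 0.63 SD.

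Power at a true difference of 0.72 SD rises from 80.0% to 81.6% (r = 0.2) or 89.9% (r = 0.5).

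**Chance imbalance.** The standard error of the baseline difference is √(2/30) = 0.26 baseline SD, so a two-standard-error imbalance is 0.52 SD. Only a fraction r of it, in SD units, reaches the outcome: 0.2 × 0.52 = 0.10 SD to 0.5 × 0.52 = 0.26 SD of the 6-month value.

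**Fewer women analysed.** The plan enlarges recruitment partly for drop-out. If only 9 × 4 = 36 women were analysed, the equivalent sizes would be 36/0.96 = 37.5 to 36/0.75 = 48. The percentages removed stay the same.

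**The case against.** A reader might infer three stronger things, and the documents support none of them.

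- **That the pre-operative POP-Q measurements are thrown away.** The preoperative list says what the data will include, which does not make it exhaustive. Stage is kept, the task table itself counts the pre-operative POP-Q as a study task, and the database fields are left to a data dictionary that is not in the documents. Office Interventions says that only the questionnaire goes beyond usual care, so POP-Q is a routine exam, and chart review is already planned; point values missing from a form might be recoverable. What stands is that the list and the table differ and should be reconciled.
- **That the plan prescribes an unadjusted ANOVA for POP-Q.** No sentence assigns the ANOVA to POP-Q; it is a general statement followed by a sentence on surgical time. Nor does the plan say whether individual points or stage will be compared. If stage is compared, pre-operative stage is the matching baseline and is already listed. What stands is that the only method stated for a continuous outcome has no baseline term, and that stage is too coarse to be the same-measure baseline for a point value.
- **That the unadjusted comparison is biased.** Mesh is randomised, so it is not. The loss is precision and protection against chance imbalance.

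It is also fair to say that POP-Q is secondary, that reoperation for recurrent prolapse and PFDI-20 also speak to support, and that at r = 0.2 the gain is negligible. Comparing several POP-Q measurements raises a multiplicity question, but it does so with or without a baseline term.

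**Conclusion.** The point holds as a low-cost improvement, not as an error that threatens the trial. A pre-operative POP-Q is scheduled for every woman, the preoperative data list names only stage, and the stated model would not use a baseline if applied to the 6-month POP-Q.

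The size depends on a correlation that the documents do not give. Over an assumed 0.2 to 0.5, adjustment removes about 4% to 25% of the residual variance, equivalent to about 62 to 80 women instead of 60 if all are analysed. The low end is hardly worth having; the upper end is material for a trial of this size. The primary outcomes and the stated sample size are unaffected.

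The same gap applies to PFDI-20: its pre-operative score is required and listed, but no stated model uses it.

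**What to change.** 1. Reconcile the preoperative list under Data Collection & Management with the task table by listing the pre-operative POP-Q point measurements as well as stage, and include them in the data dictionary.
2. Add one sentence to the Analysis Plan: each continuous 6-month POP-Q measurement will be compared between meshes with a linear model containing mesh, route and the pre-operative value of the same measurement.
3. Extend that sentence to PFDI-20, with the pre-operative score as the covariate.

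The cost is a few extra fields per woman from an exam already scheduled, and one sentence of analysis text. No visit, staff or procedure is added.
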